Ihnken et al	nken et al 1998 Adult (mean 40 Randomized to hypero 61 years) CPB (PaO2 400) vs normoxia (PaO2 140)			No adverse events reported	Statistically significant increase in oxidative stress biomarkers and myocardial damage in hyperoxic group compared to normoxia. No differences in clinical outcomes of ICU/hospital stay. Statistically significant decrease in lung function measured by PFTs in hyperoxia group 5 days post-operatively			

Overall, pediatric clinical and pre-clinical experimental studies suggest that there is a likely benefit

to normoxic and controlled re-oxygenation during cardiac surgery. However, there are several limitations

to the published data including single center studies enrolling a wide age range, heterogeneous patient

populations encompassing a wide variety of cardiac diagnoses and surgical procedures, and an inconsistent

approach to preventing early exposure to supra-physiologic oxygen levels. Furthermore, results from an

informal survey of other large pediatric cardiac surgery centers (Table 2) and survey data from 39 centers

from a large multi-institutional registry (NPC-QIC) (Figure 1) indicates that most centers utilize a supra-

physiologic oxygen management strategy and that there is significant practice variation with regards to goal

oxygen levels during cardiopulmonary bypass. Therefore, the goal of this proposed study is to investigate

the use of normoxia or near-physiologic oxygen levels before, during, and after cardiopulmonary bypass in

a well-defined, high-risk cyanotic neonatal population undergoing a select number of surgeries. The study

will be a pilot single center study to show efficacy and safety with the eventual goal of a larger multi-center

study that will be powered to show a true difference in clinical outcomes.

Table 2: Survey results from large pediatric cardiac surgery centers reporting PaO2 management on bypass practice.

PHN Center	Practice with regards to PaO2 management on Bypass				
Michigan	All patients: 200-300				
MUSC	Cyanotic patients at baseline: Initiate at 70-100 and 150 during rewarming.				
	All other patients: 150-250				
Emory	All patients: 250-300				
Boston Children's	All patients: >500				
СНОР	All patients: 200-250				
Texas Children's	All patients: Goal 150-250				
Sick Kids Toronto	All patients: Goal 120-150 on bypass				
	Cyanotic patients: Initiate bypass with PaO2<100 and then increase to goal				

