Cincinnati Children's	Cyanotic patients at baseline: Initiate bypass at 21% FiO2 and then increase to 200-250. Decrease to 80-120 prior to cross clamp removal and then goal of 200-250				
	All other patients: Maintain >200, decrease to 80-120 just prior to cross clamp removal and then 200-250 afterwards				

ANSWER CHOICES	RESPONSES
Match patient's baseline	0.00%
< 30	0.00% 0
30 - 70	0.00% 0
71 - 120	15.38% 6
121 - 200	30.77% 12
201 - 300	43.59% 17
301 - 400	2.56% 1
> 400	7.69% 3
TOTAL	39

Figure 1: Survey Data results of NPC-QIC Perfusion Practices: Goal PaO2 while on cardiopulmonary bypass.

Specific Aims:

To assess oxidative stress and end organ injury in the normoxia versus supra-physiologic oxygen groups.
 Hypothesis 1a: Normoxia will be associated with reduced oxidative stress as measured by
 thiobarbituric acid reactive substances (TBARS), a marker of lipid peroxidation. We also anticipate
 reductions in other measures including protein carbonyl, 8-isoprostane, and whole blood reduction oxidation potential.

Hypothesis 1b: End organ injury will be reduced as assessed by biomarkers of renal (Neutrophil gelatinase-associated lipocalin), neurologic (Glial fibrillary acidic protein, Tau), liver (Intestinal fatty-acid binding protein), vascular (Angiopoietin 2), and myocardial injury (Troponin I) as well as immune system activation (IL-6, IL-10).

- To evaluate the safety profile of a strategy of normoxia versus supra-physiologic oxygen.
 Hypothesis: Observed major adverse events including in-hospital mortality, cardiac arrest, need for mechanical circulatory support, seizures, and dialysis will be similar or lower in the normoxia group.
- 3. To investigate optimal endpoints in the study of the clinical impact of normoxia.

We will assess clinical endpoints that may be reflective of a reduction in oxidative stress to understand effect sizes and inform the design of subsequent trials. These endpoints will include post-operative length of stay, days alive and out of the intensive care unit (ICU) at 30 days after surgery, a composite

outcome of major adverse events as described above, and a global rank score.

Study Design:

Participants:

Single center (University of Michigan) randomized pilot study in infants less than 30 days of age

undergoing heart surgery with cardiopulmonary bypass. The trial will be unblinded with respect to

knowledge of treatment assignment as the majority of clinical personnel will have knowledge of the

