Specific Aim 1: The primary outcome for this aim will be systemic oxidative stress based on thiobarbituric acid reactive substances (TBARS), a measurement of lipid peroxidation, assessed at three separate time points in the first 24 hours after surgery. An analysis of co-variance will be used incorporating all available data to model the outcome with an adjustment for pre-operative baseline (although we anticipate no differences in baseline values by treatment arm due to randomization). The model will compare the mean values (and 95% confidence intervals) between the two groups at each time-point. In this model, we will assume missing data are missing at random, i.e., missing values may depend on observed but not unobserved data. Analysis will be performed on the basis of the intent-to-treat principle and will include an interim analysis after 24 patients are enrolled. In secondary analyses, we will use propensity scores to

account for any characteristics that were not balanced by treatment arm after randomization. We plan to

analyze other biomarkers of oxidative stress and organ injury using analogous analysis of variance models.

Specific Aim 2: To evaluate safety, we will assess the rate of observed adverse events between groups using

Chi-square test or Fisher's exact test as appropriate. Safety will also closely be monitored on a routine basis

by the Data Safety and Monitoring Board (DSMB). .

Specific Aim 3: To investigate optimal endpoints in the study of the clinical impact of normoxia. We will

assess clinical endpoints that may be reflective of a reduction in oxidative stress, including post-operative

length of stay, days alive and out of the intensive care unit (ICU) at 30 days after surgery, a composite

outcome of major adverse events as described above, and a global rank score. For all endpoints, data on

distribution within our study population and between the two groups will be calculated to understand effect

sizes and aid in planning subsequent studies.

1. Post-operative length of stay: Calculated as number of days in the hospital after surgery. May be an

attractive outcome as it can incorporate many of the morbidities that would be influenced by strategies to

reduce oxidative stress as most would lead to prolonged length of stay. The disadvantages are that it does

not incorporate mortality, and may be influenced by other center care processes and practices.

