2. Days alive and out of the ICU or hospital at 30 days after surgery: This endpoint has been used to measure

outcomes in other adult trials and a limited number of pediatric trials. It can incorporate both mortality and

various morbidities that may be influenced by strategies to reduce oxidative stress as most significant

complications or end-organ injury can extend stay in the ICU or hospital. As a continuous variable, it is

also statistically expedient allowing for smaller sample sizes to detect significant differences in treatment

groups.

3. Composite outcome: A composite endpoint can combine multiple relevant morbidities or adverse events

such as those described above. Disadvantages are that all are inherently assumed to be of equal severity.

12

ProtocolVersion: 1.4

Date: 03122021

4. Global rank score: The rank score has the advantage of allowing for the combination of various endpoints

into a single quantifiable endpoint like a composite outcome, however also allows weighting of the severity

of the component endpoints, as opposed to a traditional composite endpoint where all endpoints are treated

equally. It has been utilized increasingly in other trial settings. In this study, scores will be calculated based

on a pre-specified ranking of outcomes: mortality, cardiac arrest, ECMO, seizures, and dialysis. We will

also explore the inclusion of other clinical endpoints in both the global rank score and composite outcome,

as well as different ranking strategies.

Other secondary exploratory outcomes of general morbidity and end-organ dysfunction will be

measured and compared between the two treatment groups. Please see Table 3 for a description of the

biomarkers and other tests that will be collected or performed.

Other Secondary Exploratory Outcomes:

1. Neurologic:

a. Post-operative intracranial hemorrhage and stroke as measured by Head ultrasound

i. Alternatively, the diagnosis can be made via Head CT or MRI if clinically

indicated by the treatment team

b. Biomarkers for neurologic injury (GFAP, Tau)

c. Incidence of seizures (clinical or sub-clinical by EEG)

2. Respiratory:

a. Mechanical ventilation time (total during hospital stay)

b. Time from surgery to first extubation attempt

c. The T3 Etiometry system will be used to calculate indices of lung compliance (Tidal

volumes, mean airway pressures) on admission, 2, 6, and 24 hours after surgery (or

until extubation)

3. Heart/Circulatory system:

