B). "Unexpected". An event is considered unexpected if there are no prior data linking this
event with either the condition or intervention under study.
In terms of relation to the intervention, the Serious Adverse Event will be classified as:
a) definitely related to the intervention
b) probably related to the intervention
c) possibly related to the intervention
d) unlikely to be related to the intervention
e) definitely not related to the intervention

The clinical outcome of the Serious Adverse Event will be characterized as follows:

(a) Death

(b) Recovered: the patient returned to baseline status

(c) Symptoms continue

Data Safety Monitoring Board (DSMB)

A Data and Safety Monitoring Board will be established. The DSMB will meet 4 times a year to review

study conduct, adverse events, and any interim data.

After each DSMB meeting, a Summary Report of Adverse Events will be prepared within 30 days and will

be distributed to the Principal Investigator with instructions that the Principal Investigator forward the

Summary Report to the IRB. The Summary Report will contain the following information:

A statement that a DSMB review of outcome data, adverse events, and information relating to study

performance took place on a given date

A statement as to whether or not the frequency of adverse events exceeded what was expected and

indicated in the informed consent

A statement that a review of recent literature relevant to the research took place

The DSMB's recommendation with respect to progress or need for modification of the protocol or

informed consent. If the DSMB recommends changes to the protocols or informed consent, the

rationale for such changes and any relevant data will be provided

Reporting of Adverse Events/Serious Adverse Events

Reports of Adverse Events/Serious Adverse Events will be submitted to the local Institutional Review

Board (IRB) per institutional guidelines. The PI will report any serious adverse event to the DSMB Chair

20

as soon as possible and no later than 7 calendar days after the event.

All events/complications and all events reported as serious adverse events will be tabulated and reviewed

by the DSMB at their regularly-scheduled meetings, at least 4 times per year.

Data Collection Procedures for Adverse Events/Serious Adverse Events

1. The five events specified as Serious Adverse Events are to be reported in an expedited fashion. Any

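### Aim 2 expects major adverse events to be similar or lower with normoxia, but plans only a difference test in 21 v 21 infants and no effect measure with an interval

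*Combined protocol and SAP*

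**What the plan says.** **Hypothesis.** Under Specific Aims, Aim 2 concerns in-hospital death, cardiac arrest, mechanical circulatory support, seizures "and dialysis will be similar or lower in the normoxia group". No margin is given. The last paragraph of the Background says the study "will be a pilot single center study to show efficacy and safety", ahead of a larger multi-center trial powered for clinical outcomes.

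**Planned comparison.** Under Outcomes and Analysis, the Aim 2 paragraph reads "we will assess the rate of observed adverse events between groups using" and then names the method: "Chi-square test or Fisher's exact test as appropriate". The only other element is monitoring by the DSMB.

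**Elsewhere in the plan.**
- Aim 1 (TBARS): the model will "compare the mean values (and 95% confidence intervals) between the two groups at each time-point".
- Aim 3 covers a composite of the same events, with data on "distribution within our study population and between the two groups will be calculated to understand effect" sizes, to help plan later studies. It names no effect measure and no interval.
- The global rank score is based "on a pre-specified ranking of outcomes: mortality, cardiac arrest, ECMO, seizures, and dialysis". Seizure incidence is also compared among the secondary exploratory outcomes.
- Reporting of Adverse Events: "All events/complications and all events reported as serious adverse events will be tabulated and reviewed" by the DSMB.

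None of these states an interval for the Aim 2 events. Subject Availability sets the sample at 21 per group, 42 in total.

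**The concern.** The hypothesis has two halves, *similar* and *lower*. A chi-square or Fisher test asks whether equality can be rejected. It could support *lower* if the difference were large, but failing to reject is not evidence for *similar*, least of all with 21 infants per arm. The planned method therefore leaves out the half of the hypothesis that is most likely to be claimed.

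What is at stake is the reported safety conclusion and how designers of the larger trial use it. The planned output is group rates and a p-value, with nothing specified to show how much excess risk the data leave open. The plan does not say that p>0.05 will be read as safe, but it gives no other rule for reading the result. Protection of the enrolled infants is a separate matter: DSMB review and expedited reporting do not depend on this test.

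**Working it through.** **Inputs.** From the documents: 21 per arm, and chi-square or Fisher. Not in the documents, so assumed: two-sided 0.05, no dropout, control risks p of 10%, 15% and 20% (with 5% and 30% as outer cases), and a true doubling as the benchmark for harm. The plan has no figure for Aim 2 to reproduce; it gives no alpha, event rate, margin or power for safety.

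**Method.** Let a be events on normoxia and b events on standard of care. All 22 × 22 pairs (a, b) were enumerated, each with probability Bin(a; 21, p_N) × Bin(b; 21, p). Power is the total probability of pairs with p<0.05 when p_N = 2p. The plan's *as appropriate* was taken as the usual rule: uncorrected chi-square if every expected count is at least 5, otherwise Fisher. Both tests are also shown alone.

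**Step 1. Power to flag a true doubling**

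| Control → normoxia | Fisher | Chi-square | Usual rule |
|---|---|---|---|
| 5% → 10% | 1.9% | 5.9% | 2.0% |
| 10% → 20% | 7.9% | 14.5% | 8.9% |
| 15% → 30% | 13.2% | 21.8% | 19.1% |
| 20% → 40% | 19.1% | 31.1% | 30.5% |
| 30% → 60% | 36.0% | 49.5% | 49.5% |

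**Step 2. What a non-significant result tells us (usual rule)**

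| Control risk | P(non-significant), equal risks | P(non-significant), doubled risk | Ratio |
|---|---|---|---|
| 10% | 98.7% | 91.1% | 1.08 |
| 15% | 97.5% | 80.9% | 1.21 |
| 20% | 96.4% | 69.5% | 1.39 |

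The ratio is the first probability divided by the second, for example 98.7/91.1 = 1.08. A ratio this near 1 means that non-significance barely separates no excess from a doubling.

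**Step 3. What an interval would add.** With d = a/21 − b/21 and Wilson limits (l, u) for each arm, the Newcombe 95% interval is

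- lower: d − √[(p̂_N − l_N)² + (u_C − p̂_C)²]
- upper: d + √[(u_N − p̂_N)² + (p̂_C − l_C)²]

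For 4 control v 9 normoxia events, p̂_C = 0.190 (Wilson 0.077 to 0.400), p̂_N = 0.429 (0.245 to 0.635) and d = 0.238. The lower limit is 0.238 − √(0.184² + 0.210²) = −0.041. The upper limit is 0.238 + √(0.206² + 0.114²) = 0.473.

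| Events, control v normoxia | Fisher p | Chi-square p | Newcombe 95% interval (points) |
|---|---|---|---|
| 4 v 9 | 0.181 | 0.095 | −4.1 to +47.3 |
| 4 v 4 | 1 | 1 | −23.8 to +23.8 |
| 0 v 4 | 0.107 | 0.036 | −0.2 to +40.0 |
| 1 v 1 | 1 | 1 | −18.3 to +18.3 |
| 0 v 0 | 1 | not defined | −15.5 to +15.5 |

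For 0 v 4 the smallest expected count is 4/2 = 2, so the usual rule selects Fisher and the result is non-significant.

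**Step 4. How often a doubling remains open.** With equal true risks p, a doubling is an excess of p, so it is excluded only if the Newcombe upper limit is below p. Among non-significant results the interval still includes a doubling in 88.1%, 73.3% and 61.1% of cases at 10%, 15% and 20%. Over all equal-risk trials a doubling is excluded in 12.4%, 27.3% and 39.3%.

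**The case against.** The strongest reply is that this is a pilot. The hypothesis can be read as an expectation about observed rates and not as a formal no-worse claim. It sets no margin, no sentence says that non-significance will establish similarity, and powered clinical comparisons are left to the later trial. Low power is therefore expected, and the proposed change does not alter it. All of that is true. But safety is one of three stated aims, and a small study that cannot test should estimate. The concern is the missing estimate, not the power.

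Estimation is partly planned: rates by group, effect sizes for the composite under Aim 3, and tabulated events. Anyone with the counts can compute an interval. This stands, and it limits the weight. What remains absent is a pre-specified summary for Aim 2 and a rule for reading it.

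The contrast with Aim 1 is less sharp than it first looks, because the 95% intervals there may be around each group's mean and not around the difference. It is still true that a form of interval is named for TBARS and none for the safety events.

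Finally, the size depends on assumed rates. The composite of five events in a high-risk group, with Stage I patients included, could exceed 20%. At 30% v 60% the usual rule has 49% power, and with equal risks of 30% a doubling is excluded in 62% of trials. Even then about half of trials with a doubled risk would be non-significant. Single components are likely to be rarer than the composite, where the picture is worse.

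**Conclusion.** The concern holds. The only planned Aim 2 comparison cannot address similarity, and no effect measure with an interval is specified for these events. At 21 per arm, two-sided 0.05 and assumed control risks of 10% to 20%, a non-significant result is only 1.1 to 1.4 times as likely under equal risks as under a doubling. Observed splits as uneven as 4 v 9 would pass as non-significant. The rates and the doubling benchmark are assumptions, but the mismatch between hypothesis and method does not depend on them. It should be fixed. Its weight is minor to moderate, because it affects the reported safety conclusion and not the conduct of the trial or the monitoring of infants.

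**What to change.** In Outcomes and Analysis, Specific Aim 2, make estimation the basis of the analysis, for example:

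> For the composite and for each component we will report counts by group and the risk difference (normoxia minus standard of care) with a 95% interval suited to small samples, such as Newcombe. P>0.05 will not be read as similar safety; the upper limit will be reported as the largest excess risk not excluded.

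The chi-square or Fisher p-value may stay as a supplement. As an optional editorial change, the Background could say that the pilot will estimate safety and not show it.

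The cost is two or three sentences and a different summary of the same data. Endpoints, enrolment, treatment and data collection do not change. The downside is visibly wide intervals and a less favourable-sounding safety statement. By the figures above they would exclude a doubling in only 12% to 39% of trials with equal true risks of 10% to 20%, so the gain is an honest statement of uncertainty and not more power.

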cardiopulmonary bypass strategy based on blood gases and operative documents.

Inclusion Criteria:

• Age less than 30 days of age at time of surgery with need for cardiopulmonary bypass with

cardioplegic arrest (with or without deep hypothermic circulatory arrest)

• Diagnosis with cyanosis at baseline (pre-operative PaO2 of less than 50mmHG) due to:

o Complete admixture lesion (example: hypoplastic left heart syndrome, total anomalous

pulmonary venous return, truncus arteriosus, pulmonary atresia with VSD)

o Transposition physiology (example: D-Transposition of the great arteries or Double

outlet right ventricle with subpulmonary VSD)

o Right-to-left shunt (example: Tetralogy of Fallot, double outlet right ventricle with

suboaortic VSD and pulmonary stenosis)

Exclusion Criteria:

• Corrected gestation at time of surgery less than 37 weeks

• Prior cardiac arrest

• Current or prior history of ECMO support

• Current or prior history of needing renal replacement therapy with dialysis

• Prior cardiac surgery requiring cardiopulmonary bypass

• Diagnosis of Ebstein's Anomaly

• Known genetic syndrome other than Trisomy 21 or DiGeorge Syndrome

ProtocolVersion: 1.4 Date: 03122021

7

Subject Availability:

Based on historical data, the number of patients that fit the inclusion criteria would be about 40-50 patients

per year in this single center study. A sample size of 21 patients per treatment group (42 total patients) will

be enrolled. With a 50-67% consent rate, the study duration will be approximately 24 months.

Trial Enrollment and Randomization:

Infants will be randomized into two groups:

1. Normoxia Group (with controlled re-oxygenation):

a. Goal PaO2 on cardiopulmonary bypass of 60-100 mm Hg using lower FiO2 (blended

sweep gas) via oxygenator

b. Post-bypass, goal of PaO2 < 100 mm Hg by anesthesia and in ICU via oxygen titration via

mechanical ventilator for 24 hours post-op.

2. Standard of Care Group: Current standard of care

Randomization will be performed in random permuted block sizes of 2 or 4 and stratified by "Stage I

Palliation" (Norwood arch reconstruction with shunt placement [Right ventricle-to-pulmonary artery shunt,

modified Blalock-Taussig shunt, or central aortopulmonary shunt]) in each treatment group. Patients

undergoing Stage I palliation are known to have higher rates of complications and mortality at baseline and

therefore the stratification will be done to control for this in the randomization.

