Study Protocol:

Please see Figure 2 for a summary of the study protocol.

1. Preoperative:

Patients that meet the defined inclusion and exclusion criteria will be identified and the families will be

8

approached for consent prior to the scheduled surgery.

Patients that are enrolled in the study will have the following pre-operative studies:

ProtocolVersion: 1.4

Date: 03122021

• Head ultrasound (not currently standard of care but will be used to evaluate for any brain injury

in each group)

• Renal function and liver function panel (within 24 hours prior to surgery)

2. Operating Room:

Patients will be brought to the operating room in a standard fashion. Anesthesia will induce general

anesthesia per protocol and secure an airway (if needed) and place invasive lines. Patients will have labs

drawn (baseline biomarkers of oxidative stress, troponin level, and Redox potential) and an arterial blood

gas.

All patients will have a median sternotomy and be cannulated onto cardiopulmonary bypass via standard

procedures at the discretion of the surgery team.

3. Initiation of Cardiopulmonary Bypass:

The cardiopulmonary bypass circuits will be set up and primed per standard institutional protocols.

"Normoxia" Group: Prior to cannulation, a blood gas will be drawn from the cardiopulmonary bypass

circuit and correlated to the CDI (in-line PaO2 monitor). The FiO2 of the oxygenator will then be titrated

to achieve a PaO₂ of the circuit and CDI of 60-100 mm Hg. After cannulation, frequent blood gases will

be checked per protocol and correlated with the CDI to maintain a PaO₂ of 60-100 mm Hg.

"Standard of Care" Group: After cannulation, frequent blood gases will be checked per protocol on bypass

and correlated with the CDI to maintain a PaO₂ of 200-300 per standard practice.

4. Weaning of Cardiopulmonary Bypass:

At the end of re-warming, a blood sample will be obtained for appropriate studies.

"Normoxia" Group: As cardiopulmonary bypass is being weaned, anesthesia will initiate mechanical

ventilation with an FiO2 of 50% or less (unless clinically necessary) to achieve oxygen saturation and PaO2

9

goals that fit within the expected range for the patient's physiology:

1. Single ventricle patients (PaO₂:35-45 and oxygen saturation 75%-85%)

2. Two ventricle patients (PaO₂: 60-100 and oxygen saturation >92%)

ProtocolVersion: 1.4

. . .

Measures of oxygen delivery such as NIRS monitoring, mixed venous oxygen saturations, and

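### Permuted blocks of 2 or 4 within two strata, in an open single-centre trial, let anyone keeping a tally per stratum guess the next arm about 71–72% of the time

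*Combined protocol and SAP*

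**What the plan says.** Under Trial Enrollment and Randomization the protocol specifies: "Randomization will be performed in random permuted block sizes of 2 or 4", with Stage I palliation (yes or no) as the only stratification factor, because these infants have more complications and deaths. There are two arms: "A sample size of 21 patients per treatment group (42 total patients) will" be enrolled.

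Study Design, Participants describes one centre and declares: "The trial will be unblinded with respect to" "knowledge of treatment assignment as the majority of clinical personnel will have knowledge of the" bypass strategy, which they will learn from gas results and operating records.

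Study Protocol, Preoperative has families "approached for consent prior to the scheduled surgery". Subject Availability adds: "With a 50-67% consent rate, the study duration will be approximately 24 months".

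The documents do not say who generates or holds the list, how the next assignment is concealed, or whether randomization comes before or after consent. They do not give the probability of each block size or the expected size of the Stage I stratum. Under Outcomes and Analysis, Specific Aim 1, the analysis of covariance adjusts for the pre-operative baseline only; the stratification factor is not mentioned.

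**The concern.** In an open trial, concealing the next assignment is what keeps recruitment independent of treatment. Short blocks weaken this, because each must return to balance quickly: once one arm is ahead in a stratum, the other is more likely to come next.

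The information needed is at hand here. One team sees every completed case, and the two bypass oxygen targets (PaO2 60–100 against 200–300 mm Hg) do not overlap, so each case reveals its arm. Stage I status follows from the planned operation, so a tally per stratum is easy to keep.

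If the decision to approach a family, or its timing, were influenced by the expected arm, the groups could differ in risk from the start. With 21 infants per arm, steering a few high-risk infants could distort both the safety comparison and the effect sizes meant to inform a larger trial.

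**Working it through.** The documents state no guess probability, so there is no plan figure to reproduce.

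**Inputs from the protocol.** Block sizes 2 or 4; two strata; two arms; 21 + 21 = 42 infants.

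**Assumptions.** Each block is equally likely to be of size 2 or 4 (other mixes shown). Stage I stratum of 5, 10, 14 or 21 of the 42. The guesser knows all past assignments in the stratum.

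**Step 1: best guess in the long run.** Guess the arm that is behind in the stratum, and toss a coin when the arms are tied (the Blackwell–Hodges convergence strategy). Expected correct guesses in a block of size 2n are n + (4^n / C(2n, n) − 1)/2.

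- Block of 2: 1 + (4/2 − 1)/2 = 1.5, and 1.5/2 = 75.0%.
- Block of 4: 2 + (16/6 − 1)/2 = 17/6, and (17/6)/4 = 70.8%.
- Equal mix: (3/2 + 17/6)/6 = 72.2%.
- Twice as many 4s: (3/2 + 2 × 17/6)/10 = 71.7%.
- Twice as many 2s: (2 × 3/2 + 17/6)/8 = 72.9%.
- Limits for any mix: 70.8% to 75.0%.

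**Step 2: this trial.** Simulating 42 infants in two strata, with incomplete last blocks, gives 71.1–71.9% across the assumed stratum sizes. Someone who tracks only the overall tally and ignores strata would be right about 65–66% of the time.

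**Step 3: fully certain assignments, sizes known.** A lead of 2 can arise only inside a block of 4, and the next two assignments are then forced. This happens in 2 of the 6 arrangements of a block of 4, so it gives 2 × 1/3 = 2/3 of an assignment per block of 4. Over an equal mix that is (2/3)/6 = 11%; with finite strata it is about 10%.

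**Step 4: alternatives.** For 4/6, a block of 6 gives 3 + (64/20 − 1)/2 = 4.1 correct guesses, so the long-run rate is (17/6 + 4.1)/10 = 69.3%. The table simulates strata of 14, 21 and 28 infants with an optimal Bayesian predictor who knows the scheme.

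| Scheme within stratum | Best-guess accuracy | Predictable with ≥75% certainty | Fully certain |
|---|---|---|---|
| Blocks 2/4 (plan) | 71–72% | 53–55% | about 10% |
| Blocks 4/6 | 68–69% | 43–47% | about 6% |
| Big stick, limit 2 | 61–62% | 21–24% | 21–24% |
| Big stick, limit 3 | 57–58% | 13–15% | 13–15% |

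A big stick tosses a fair coin until the arm difference in the stratum reaches the limit, then forces the arm that is behind. Every one of its assignments above the 75% threshold is therefore fully certain.

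**Step 5: balance cost of big stick, limit 3.** Mean final imbalance per stratum is 1.3–1.7 infants, against 0.2–1.0 under 2/4. With strata of 14 and 28, a 23:19 split occurs in about 22% of trials, against about 0.7% under 2/4, and is the worst possible. Its relative efficiency is 4 × 23 × 19 / 42² = 1748/1764 = 99.1%, a loss under 1%. If both strata end odd-sized, the limit allows 3 + 3 = 6, that is 24:18, with efficiency 4 × 24 × 18 / 1764 = 98.0%.

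**The case against.** Short stratified blocks are a recognised trade of predictability for balance. In a pilot of 42 with a laboratory primary outcome, an interim analysis at 24 patients and a stated wish to balance Stage I infants, the choice is defensible. Moving to 4/6 gains only about 3 points of accuracy, and a big stick raises the share of fully certain assignments, which are the easiest to exploit. All of this stands. It is why the change is a cheap improvement and the big stick only an option.

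A reader might infer more than the documents support, in four ways.

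- **That printing the sizes produces the 72%.** It does not. Following the lagging arm requires only past assignments; hiding the sizes mainly removes the certainty.
- **That the expected consent rate shows staff choosing whom to enrol.** It describes family consent. Deferral also has limited room: eligibility ends at 30 days of age, and 42 infants in about 730 days is one every 17 days or so.
- **That assignments are therefore known in advance.** The 71–72% is an average for an ideal guesser keeping a tally per stratum; about nine in ten assignments remain uncertain.
- **That no analysis could help.** Baseline TBARS adjustment and the secondary propensity-score analyses address measured differences in part. Selection on unmeasured features would remain.

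Selective approach is still possible, and nothing described in the plan would prevent it.

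**Conclusion.** The point holds as an avoidable weakness, not as a demonstrated bias. With equally likely block sizes and a guesser who tracks each stratum, accuracy averages 71–72% in a trial of this size, some 21–22 points above chance. It stays well above chance, at 65–66%, for someone who ignores strata. About 10% of assignments are fully certain if the sizes are known.

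Selection bias would require someone involved in approaching families to act on the guess. The documents give no evidence of that, but they also name no list-holder, concealment method or order of consent and randomization. Because the remedy costs little and lowers every measure of predictability examined, it should be made, but the present scheme does not invalidate the trial.

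**What to change.** **Recommended.** Remove blocks of 2 (for example, use 4 and 6) and move the block sizes from the protocol to a restricted randomization document. With sizes known, 4/6 alone lowers best-guess accuracy to 68–69%, certain assignments to about 6% and those predictable at 75% or more to 43–47%; hiding the sizes mainly removes the certainty that remains. The cost is a new list, a sentence in the protocol and slightly looser balance.

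**Optional, for a larger reduction.** Use a big-stick design with limit 3 within each stratum (57–58% accuracy). The price is 13–15% forced assignments and about a 22% chance of a 23:19 split, assuming strata of 14 and 28.

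**In either case.** Add the Stage I stratum to the Specific Aim 1 analysis of covariance. This is a separate change to the model text, needed so that any within-stratum imbalance is accounted for.
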